I understand that the Sponsor may decide to suspend or prematurely terminate the study at any time for whatever reason; such a decision will be communicated to me in writing. Conversely, should I decide to withdraw from execution of the study, I will communicate my intention immediately in writing to the Sponsor.

_____ Print Name	_____ Signature
_____ Investigator Title	_____ Date (DD MMM YYYY)

PROTOCOL SYNOPSIS

Protocol Number:	ALT-FLZ-401
Product:	Fluzone Intramuscular Quadrivalent vaccine
Active Ingredient(s)/INN:	Vaccine
Study Title:	Extent and Durability of Immune Response Following Seasonal Influenza Vaccination in Healthy Volunteers
Study Phase:	Phase 4
Indication Under Investigation:	Influenza
Study Objectives:	
Primary Objective
 
To evaluate antibody response against matched influenza strains as measured by hemagglutination inhibition (HAI) following administration of a seasonal influenza vaccine.
 
Secondary Objectives
 
To evaluate 1) antibody responses to divergent influenza strains 2) cellular immune responses and 3) mucosal antibody responses following administration of seasonal influenza vaccine (Fluzone Quadrivalent)

Study Design:	
This will be an open-label, single administration dose study in adult healthy male and female subjects. After qualifying for the study, subjects will receive a single intramuscular injection of the FDA approved 2016-2017 quadrivalent influenza vaccine.
 
Subjects will be screened within 28 days prior to enrollment into the study. After qualifying for the study subjects will visit the clinical unit on Day 1 and will have pre-dose blood samples taken for humoral (serum) and cellular (peripheral blood mononuclear cells PBMCs) immunity testing and nasopharyngeal swabs for assessment of mucosal immunity, and will then be given the vaccine. Over the next 6 months, 10-mL blood samples will be collected on Days 4, 8, 15, 29, 91 and 181 for HAI testing. Peripheral blood mononuclear cells will be collected on Day 8 to assess cellular responses. A nasopharyngeal swab will also be done on Day 29. Screening assessments will include clinical laboratory tests (hematology, chemistry, urinalysis

	[UA], drug and alcohol testing), vital signs, 12-lead electrocardiogram and physical examination. Adverse events (AEs) will be monitored throughout the study.
Study Duration:	The duration of the study for each individual subject will be up to 7 months from the start of Screening (within 28 days of dosing). Dosing will be on a single occasion with follow-up for 6 months.
Study Sites and Location:	The study will be conducted at: Optimal Research, Rockville MD
Planned Sample Size:	20 healthy subjects will be enrolled and receive a single dose of the vaccine.
Subject Eligibility Criteria:	Inclusion Criteria: 
1. Men and women 18 to 50 years of age, inclusive2. Good general health status, as determined by the Investigator3. Adequate venous access for repeated phlebotomies4. Screening laboratory results within institutional normal range or Grade 1 elevation if the Investigator documents clinical insignificance. Bilirubin may be Grade 2 if associated with normal alanine aminotransferase (ALT) and aspartate aminotransferase (AST) and the Investigator considers the result not to be clinically significant (e.g. vigorous exercise or Gilbert's syndrome)5. Negative drug and alcohol screen at Screening and predose on Day 16. For women of child bearing potential, negative pregnancy test7. Willingness to practice a highly effective method of contraception that may include, but is not limited to, abstinence, sex only with persons of the same sex, monogamous relationship with a postmenopausal partner, monogamous relationship with vasectomized partner, vasectomy, surgical sterilization (hysterectomy, or bilateral tubal

ligation, salpingectomy, or oophorectomy), licensed hormonal methods, intrauterine device (IUD), or consistent use of a barrier method (e.g., condom, diaphragm) with spermicide for 28 days after the Fluzone Intramuscular Quadrivalent vaccine dose

8. Willingness to participate and comply with all aspects of the study through the entire study period, including nasal swabs and blood samples
9. Provision of written informed consent

Exclusion Criteria:

1. Pregnant, possibly pregnant, or lactating women
 2. Body mass index $> 35.0 \text{ kg/m}^2$
 3. Positive results for HIV, hepatitis B virus, or hepatitis C virus at Screening
 4. Asthma or other chronic lung disease that is greater than mild in severity. Specifically excluded are participants with any of the following events in the past year:
 - Daily symptoms
 - Daily use of short acting beta 2 agonists
 - Use of inhaled steroids or theophylline
 - Use of pulse systemic steroids
 - Emergency care or hospitalization related to asthma or other chronic lung disease
 - Systemic steroids for asthma exacerbation
 5. History of diabetes mellitus (gestational diabetes is allowed if treatment was not required postpartum and serum glucose is currently in the normal range)
 6. History of coronary artery disease, arrhythmia, or congestive heart failure
 7. Clinically significant ECG abnormality
-

8. Poorly controlled hypertension (systolic blood pressure > 150 mmHg or diastolic blood pressure > 95 mmHg) at Screening or predose on Day 1
 9. History of anaphylaxis or angioedema
 10. Known allergy to any of the ingredients in the vaccine formulation including egg allergy
 11. History of chronic rhinitis, nasal septal defect, cleft palate, nasal polyps, or other nasal abnormality that might affect vaccine administration
 12. Previous nasal surgery or nasal cauterization
 13. Any symptoms of upper respiratory infection or temperature > 38°C within 3 days before Day 1
 14. Significant nasal congestion or rhinorrhea as assessed by the investigator.
 15. Known or suspected malignancy, excluding non-melanoma skin cancers and other early stage surgically excised malignancies that the Investigator considers to be exceedingly unlikely to recur
 16. Immunocompromised individuals, including those who have used corticosteroids (including intranasal steroids), alkylating drugs, antimetabolites, radiation, immune-modulating biologics, or other immunomodulating therapies within 90 days before Day 1 or those who plan use during the study period
 17. Use of statin medication within 30 days before Day 1 (including atorvastatin, fluvastatin, lovastatin, pravastatin, rosuvastatin, simvastatin, pitavastatin)
 18. Receipt of intranasal medications (including over-the-counter medications) within 30 days before Day 1
 19. Receipt of any IP within 30 days before Day 1
-

20. Receipt of any vaccine within 30 days before Day 1
 21. Receipt of intranasal vaccine within 90 days before Day 1
 22. Receipt of any influenza vaccine within 6 months before Day 1
 23. Any change in medication for a chronic medical condition within 30 days before Day 1
 24. Past regular use or current use of intranasal illicit drugs or any regular use of illicit drugs by any other route.
 25. Use of tobacco products or electronic cigarettes within 30 days before Day 1. Any other smoking products including marijuana will be excluded.
 26. Any medical, psychiatric, or social condition or any occupational or other responsibility that in the judgment of the Investigator would interfere with or serve as a contraindication to protocol adherence, assessment of safety (including immunogenicity), or a subject's ability to give informed consent
-

Dosage Form, Dose and Route of Administration:

- Solution dose (0.5 mL), intramuscular
-

Study Endpoints:

Efficacy (immunogenicity)

Antibody and cellular immune responses following seasonal influenza vaccination

Safety

AEs

Statistical Analyses:

Sample Size Determination

Based on practical considerations, 20 subjects will be enrolled.

Safety

For safety, the primary assessment will be adverse event rate, type of adverse event, severity.

TABLE OF CONTENTS

1.	INTRODUCTION.....	13
1.1	Study Rationale	13
1.2	Risks and Benefits for Study Subjects	13
1.3	Population, Route, Dosage, Dosage Regimen, Treatment Period.....	14
1.4	Compliance Statement, Ethics and Regulatory Compliance.....	14
1.4.1	Subject Confidentiality.....	14
1.4.2	Informed Consent Procedure.....	14
1.4.3	Regulatory Compliance.....	15
2.	STUDY OBJECTIVES	16
2.1.	Primary Objective.....	16
2.2.	Secondary Objectives	16
3.	STUDY DESIGN	17
3.1	Overall Plan.....	17
3.1.1.	Study Type	17
3.1.2.	Treatment Groups.....	17
3.1.3.	Study Endpoints	17
3.1.4.	Duration of the Study	17
3.1.5.	Duration of Subject Participation.....	17
3.2	Selection of Dose.....	17
4.	STUDY POPULATION.....	18
4.1	Enrollment	18
4.2	Inclusion and Exclusion Criteria	18
4.3	Removal of Subjects From Therapy.....	20
4.3.1.	Reasons for Withdrawal/Early Discontinuation.....	20
4.3.2.	Withdrawal Procedures	21
4.3.3.	Subject Replacement	21
5.	TREATMENTS ADMINISTERED.....	22
5.1	Investigational Products	22

5.2.	Method of Assigning Subjects to Treatments and Blinding.....	22
5.3.	Method of Assessing Treatment Compliance.....	22
5.4.	Labeling and Packaging	22
5.4.1.	Preparation.....	22
5.4.2.	Storage Conditions	22
5.4.3.	Drug Accountability	22
5.4.4.	Retention Samples	23
5.5.	Concomitant Medications.....	23
5.6.	Lifestyle Guidelines	23
6.	STUDY PROCEDURES.....	24
6.2	Randomization.....	24
6.3	Treatment Period	24
6.3.1	Day 1	24
6.4	End-of-Study	26
6.5	Follow-up	26
6.6	Protocol Deviations	26
7.	EFFICACY ASSESSMENTS	27
8.	IMMUNOGENECITY ASSESSMENTS	28
9.	PHARMACOKINETIC ASSESSMENTS..... ERROR! BOOKMARK NOT DEFINED.	
10.	SAFETY ASSESSMENTS	31
10.1.	Adverse Events.....	31
10.2.	Safety Variables	31
10.3.	Definitions	31

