1. INTRODUCTION

Influenza is a major cause of morbidity and mortality worldwide with the elderly being at highest risk of complications and death. Seasonal flu vaccines are designed to protect against infection and illness caused by the flu viruses research indicates will be most common during the flu season. “Quadrivalent” flu vaccines are formulated to protect against four flu viruses, but do not protect against infection and illness caused by other viruses that can also cause flu-like symptoms. There are many other viruses besides flu viruses that can result in flu-like illness (also known as influenza-like illness) that spread during the flu season. These non-flu viruses include rhinovirus (one cause of the "common cold") and respiratory syncytial virus, which is the most common cause of severe respiratory illness in young children, as well as a leading cause of death from respiratory illness in those aged 65 years and older.

Fluzone Quadrivalent is a vaccine indicated for active immunization for the prevention of influenza disease caused by influenza A subtype viruses and type B viruses contained in the vaccine (1). It is approved in US for use in persons 6 months of age and older.

Antibody protection is traditionally measured by hemagglutinin-inhibition (HAI), where antibodies to the virus block the function of hemagglutinin to prevent viral attachment to host cells. It is believed that HAI antibody levels closely correlate with virus neutralization assays, however, it should not be considered a marker of efficacy (2).

The Safety profile of the Quadrivalent vaccine is similar to seasonal flu vaccines made to protect against three viruses, with similar mild side effects (injection site pain, malaise, headache).

This study is being undertaken to evaluate antibody and cellular immune responses to various influenza strains following seasonal influenza vaccination. Blood samples collected at 1 week and at various intervals up to 6 months post vaccination will be analyzed for assessment of cellular and antibody responses to the vaccine. Nasopharyngeal swabs collected at baseline and 4 weeks following immunization will be used to assess mucosal antibody response to influenza.

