2. STUDY OBJECTIVES

2.1. Primary Objective

The primary objective of this study is:

To evaluate the antibody response as measured by HAI following administration of the approved Fluzone Intramuscular Quadrivalent vaccine.

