
 To evaluate the mucosal immune response NasoVAX when administered by intranasal spray at a single dose of 1×10^9, 1×10^{10}, or 1×10^{11} vp 	
 Immunoglobulin A (IgA) antibody level measured by enzyme-linked immunosorbent assay (ELISA): 
 GMT GMR

 To evaluate the humoral immune response against nonrepresented influenza strains after NasoVAX administration 	
 Antibody level measured by HAI and MN in serum against each strain tested: 
 GMT GMR Responder rate: the number and percentage of subjects with 2-fold and 4-fold rise since baseline

 To evaluate the effect of predose adenovirus serotype 5 (Ad5) serum antibody levels on the immunogenicity of NasoVAX 	
 Predose Ad5 antibody GMT measured by MN in serum Day 29 GMR and responder rate from antibody level measured by HAI in serum

 To compare immunogenicity results to those obtained from banked samples from a previous study of licensed seasonal vaccine in a similar subject population (ALT-FLZ-401) 	
 Antibody level measured by HAI in serum: 
 GMT GMR SPR SCR Antibody level measured by MN in serum: 
 GMT Responder rate SFUs to hemagglutinin peptides measured by ELISpot in PBMCs: 
 Geometric mean SFUs Responder rate IgA antibody level measured by ELISA: 
 GMT GMR

4 Study Design

Study ALT-103-201 is a Phase 2a, randomized, double-blind, placebo-controlled trial to evaluate the safety, and immunogenicity of NasoVAX in healthy adults 18 to 49 years of age. Subjects will be screened within 28 days of randomization (Day 1). Approximately 60 subjects who meet all inclusion and no exclusion criteria and provide written informed consent will be enrolled into 3 sequential cohorts of 20 subjects each defined by the viral particle dose (1×10^9 , 1×10^{10} , and 1×10^{11} vp). Within each cohort and its sentinel group, subjects will be randomized in a 3:1 ratio to receive 1 intranasal dose of NasoVAX or placebo (Day 1) as shown in Table 4-1.

Table 4-1 NasoVax Study Design

Cohort	Dose (vp)	Number of Subjects	
		NasoVAX	Placebo
1	1×10^9	15	5
2	1×10^{10}	15	5

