3	1×10^{11}	15	5
Study Total Target		45	15
Total		60	

A sentinel group of 5 subjects from each cohort will be dosed. Dosing of the remainder of each cohort may proceed after the last sentinel subject completes Day 8 if no events meeting stopping criteria have occurred. The Safety Review Committee (SRC), consisting of the Investigator, the Medical Monitor, and a Sponsor Representative, will review AE, reactogenicity, and laboratory data through at least Day 8 for all subjects in each cohort before subjects are randomized to the next higher dose. If any event meeting stopping criteria occur, the SRC will review all available safety information before additional patients are dosed. Stopping criteria are as follows, using the Food and Drug Administration (FDA) toxicity grading scale [1]:

- Occurrence of any related SAE or Grade 4 AE
- Occurrence of 2 Grade 3 AEs in the same organ system
- Occurrence of the same Grade 3 laboratory abnormality in 2 or more subjects

Each subject will record local events, systemic events, and oral temperature in a diary daily for 14 days after the NasoVAX/placebo dose. Each subject will be contacted by telephone on Day 2 for safety assessment and review of the diary. Subjects will return to the investigational site on Days 4, 8, 15, 29, 91, and 181 for safety and immunogenicity assessments.

A serum sample will be collected from each subject for evaluation of influenza HAI assay against A/California/04/2009 predose on Day 1 on Days 4, 8, 15, 29, 91, and 181; Ad5 antibody, MN assay against both A/California/04/2009(H1N1) and nonrepresented strains, and HAI against nonrepresented strains will also be evaluated at Days 1 and 29. A whole

blood sample will be collected from each subject and processed to isolate PBMCs for evaluation of T-cell responses by ELISpot predose on Day 1 and on Day 8.

A nasopharyngeal swab sample will be collected from each subject at Screening and on Days 4, 8, 15, 29, and 91 to measure concentration of the Ad5 vector for assessment of vaccine vector shedding by quantitative polymerase chain reaction (qPCR) assay. Once a negative result is obtained, later samples may not be tested. ELISA for measurement of IgA will also be performed on the swab samples from Screening and Day 29 for evaluation of mucosal immune response.

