All AEs and medications will be recorded from signing of the informed consent form to Day 29. Thereafter to the end of the study, only MAEs, NCIs, SAEs, immunosuppressive medications (see list in Appendix 3), and vaccines will be recorded. Samples for clinical laboratory tests (hematology, serum chemistry, urinalysis) will be collected at Screening and on Days 8 and 29. A complete physical examination and vital signs will be performed at Screening and predose on Day 1, and targeted and symptom-driven physical examinations will be performed and vital signs measured 2 hours postdose and on Days 4, 8, 15, and 29. An electrocardiogram (ECG) will be performed at Screening and on Day 29. If a subject experiences acute symptoms compatible with adenoviral infection within 28 days after the NasoVAX/placebo dose, a sample will be collected for viral culture as clinically indicated.

One interim analysis of humoral immunogenicity data and safety data (including summaries of AE, reactogenicity, concomitant medications and vaccines, vital signs, ECG, and laboratory data and listing of any viral culture results) will be conducted when all data through the Day 29 visit is available and monitored for all subjects.

A complete schedule of procedures and assessments for study ALT-103-201 is in Table 4-2.

ALT-FLZ-401, Extent and Durability of Immune Response Following Seasonal Influenza Vaccination in Healthy Volunteers, was an open label study designed to generate an immunogenicity sample set similar to that of ALT-103-201 in subjects receiving a licensed influenza vaccine based on the same H1 strain (A/California 2009). The seasonal vaccine H1 component changed at the time of the ALT-103-201 study to A/Michigan, so it was logistically much easier to conduct this study non-contemporaneously with the seasonal vaccine licensed for use in 2016-17. The same site, entry criteria and schedule of assessments for immunogenicity were followed. Twenty subjects were enrolled and samples from this study were frozen and stored and then shipped to blinded laboratory for immunogenicity testing in parallel to the samples from ALT-103-201. The schedule of events for ALT-FLZ-401 is in Table 4-3.

Table 4-2. ALT-103-201 TIME AND EVENTS SCHEDULE

Study Visit	Screening	Dosing Period							Follow-up Period	
		Day 1		Day 2 ^a	Day 4	Day 8	Day 15	Day 29	Day 91	Day 181
Window (days)	Day -28 to Day -1	Predose	Postdose		± 1	± 1	± 1	± 3	± 10	± 10
Informed consent	X									
Demographics	X									

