8.6 Immunogenicity Analysis

All immunogenicity analyses will be conducted on the PP Population. Analyses based on the ITT Population will be undertaken and presented only if >5% of subjects in any 1 dose group were excluded from the PP Population. Summaries and analysis will be completed by dose group and overall for subjects on an active NasoVAX dose.

The variables that will be analyzed, and the endpoints generated for each variable, are listed in Table 8-1:

Table 8-1. Immunogenicity Variables and Endpoints

Variable Name	GMT	GMR	SPR	SCR	Responder Rate	Geometric Mean SFUs	Compare to ALT-FLZ-401
A/California 2009 antibody level measured by HAI in serum	X	X	X	X			X
A/California 2009 antibody level measured by MN in serum	X	X			X		X
Cellular response to A/California 2009 peptides measured by enzyme-linked ELISpot in PBMCs					X	X	X
IgA antibody level measured by ELISA in nasopharyngeal swab	X	X					X
Antibody level measured by HAI in serum against the following nonrepresented strains: - A/Brisbane/59/2007 (H1 strain) - A/Saint-Petersburg/61/2015 (H1 strain) - A/New Jersey/76 (H1 strain) - A/Perth/16/2009 (H3 strain) - A/Vietnam/1203/2004XPR8 (H5 strain)	X	X			X		X
Antibody level measured by MN in serum against nonrepresented strains	X	X			X		X
Ad5 antibody levels in serum	X	X			X		

Note: Refer to Section 3 for descriptions of each endpoint.

Assay data will be tabulated by visit using the applicable endpoint(s) (e.g., GMT, GMR, or geometric mean SFUs) and their 95% CIs. Graphical representations of the longitudinal immune responses will also be given.

[figure not shown]
Analysis of covariance (ANCOVA) will be used in the analysis of the antibody levels at each post-baseline visit, with log-transformed antibody level as dependent variable, dose group as a factor, and baseline log-transformed level as a covariate. This model will be generated using SAS Proc Mixed with dose group in the CLASS statement and visit in the BY statement. Comparisons of post-baseline log-transformed antibody level will be conducted for each NasoVAX dose group against the placebo group and against the Fluzone group, if applicable. Least square (LS) means and 95% CI of the LS means of dose group, difference of LS means and 95% CI of the difference in LS means will be

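### Does planning full HAI endpoints for one H1 virus leave the four-virus primary objective of ALT-FLZ-401 unanswered without saying so?

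*Protocol*

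**What the plan says.** The protocol words the primary objective in two ways. The synopsis has "To evaluate antibody response against matched influenza strains as measured by hemagglutination inhibition (HAI) following administration of a seasonal influenza vaccine". Section 2.1 has "To evaluate the antibody response as measured by HAI following administration of the approved Fluzone Intramuscular Quadrivalent vaccine", with no mention of matching or of strains. Section 1 says that quadrivalent "flu vaccines are formulated to protect against four flu viruses" and that this product is indicated against "influenza A subtype viruses and type B viruses contained in the vaccine". The immunogenicity endpoint in Section 3.1.3.1 is generic and names no virus.

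The SAP is written for ALT-103-201, the NasoVAX dose-ascending trial. ALT-FLZ-401 enters under an exploratory objective in SAP Section 3, a comparison with "banked samples from a previous study of licensed seasonal vaccine in a similar subject population (ALT-FLZ-401"). SAP Section 4 describes ALT-FLZ-401 as a matching sample set from recipients of a "licensed influenza vaccine based on the same H1 strain (A/California 2009"), and says why that season's vaccine was used.

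In SAP Section 8.6, Table 8-1, the row "A/California 2009 antibody level measured by HAI in serum" carries GMT, GMR, SPR and SCR and is marked for comparison with ALT-FLZ-401. A second HAI row lists five nonrepresented strains, with GMT, GMR and responder rate only. For these, Section 4 states that "HAI against nonrepresented strains will also be evaluated at Days 1 and 29". Section 7.4.1 declares one change, to the per-protocol definition, and otherwise claims consistency with the analyses in the study protocols.

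**The concern.** The synopsis uses a plural, the vaccine covers four viruses, and the SAP gives the complete HAI treatment to one of them. The protocol also separates matched strains (primary) from divergent strains (secondary). The nonrepresented panel therefore looks like the secondary objective, which leaves a single identified virus for the primary one. No type B virus appears in the HAI plan at all.

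Section 7.4.1 is where a narrowing of this kind would normally be declared, and it refers to protocols in the plural, so it takes in ALT-FLZ-401. Protocol Section 1.4.3 adds that changes to the planned analysis belong in an amendment. If a result for H1 were reported as the answer to an objective covering the whole vaccine, the claim would be broader than the data.

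**Working it through.** No sample-size, power or alpha figure bears on this point. The 20 subjects rest on practical considerations, so there is no stated calculation to reproduce. The check is a count and a comparison of texts.

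**Count of HAI strains (SAP Table 8-1)**

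| Subtype | Strains | Number |
|---|---|---|
| H1 | A/California 2009, A/Brisbane/59/2007, A/Saint-Petersburg/61/2015, A/New Jersey/76 | 4 |
| H3 | A/Perth/16/2009 | 1 |
| H5 | A/Vietnam/1203/2004 | 1 |
| Type B | none | 0 |

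The total is 4 + 1 + 1 + 0 = 6.

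**Coverage of the vaccine.** The denominator is 4 viruses (Protocol Section 1).

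- Identified in the SAP as a component of the licensed vaccine: A/California 2009, so 1/4 = 25% have full HAI endpoints and 3/4 do not.
- If A/Perth/16/2009 is also a component (an assumption), coverage is 2/4 = 50%. The second virus would then have Days 1 and 29 only, without SPR or SCR.
- The assumption cannot be settled here. Protocol Appendix 15.3 attaches the 2016-2017 package insert, whose contents list a description section, but that section is not readable in the copy reviewed. Composition therefore cannot be called undocumented.

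**Does the SAP undertake to answer the ALT-FLZ-401 primary objective?** SAP Section 3 lists primary, secondary and exploratory objectives. All concern NasoVAX, and ALT-FLZ-401 appears only as the comparator in the last exploratory one. For that comparison the virus common to both vaccines is the natural target, and Section 4 identifies it as H1.

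**Does the SAP depart from an analysis in the ALT-FLZ-401 protocol?** Section 7.4.1 speaks of described analyses. The protocol's synopsis entry on statistics covers sample size and safety only, the body has no statistics section, and the endpoint names no strain. An objective is stated, but no strain-level HAI analysis is described, so there is none to depart from.

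**Can a reader see the restriction?** Yes. Table 8-1 names A/California 2009, and so do the titles of Table 14.4.1.1 and Figure 14.4.1.1 in SAP Section 10.1.

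**What would a declaration change?** The visit-wise GMT, GMR, SPR and SCR with their 95% CIs, the ANCOVA and Fisher comparisons, and the output titles would all stay as they are.

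**The case for a change.** The strongest opposing case is that the SAP cites the ALT-FLZ-401 protocol as reference material, treats its subjects as an added arm, and claims consistency with both protocols. No other immunogenicity plan for ALT-FLZ-401 is supplied. Section 4 explains why the H1 comparison makes sense but never says that the ALT-FLZ-401 objective is thereby addressed only in part. The absence of type B viruses needs no outside knowledge to establish, and one sentence would cost nothing.

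The facts in this stand: the count is correct, the cross-reference is missing, and Section 2.1 is no narrower than the synopsis. The consequence does not follow. The multi-strain commitment rests on one plural in the synopsis. Nothing in the protocol defines matched or promises HAI on all four components. The outputs carry the name of the virus, so an H1 result is labelled as one. Whether a separate ALT-FLZ-401 analysis exists cannot be known from these files, and its absence from them is not evidence that none was planned.

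Answering the objective for the other viruses would take further assays, which wording cannot supply. ALT-103-201 draws a larger serum sample on Days 1 and 29 for additional assays (SAP Table 4-2, footnote e), whereas ALT-FLZ-401 draws 10 mL at each visit (Protocol Section 6.3.1). Residual serum and budget are therefore not assured. Protocol Section 8 already leaves room for later immunogenicity work on retained samples from subjects who consent to it.

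**Conclusion.** No change follows. The SAP covers 1 of the 4 vaccine viruses with full HAI endpoints (2 of 4 at most, with reduced endpoints for the second) and names no type B strain. This is a sensible scope for an exploratory H1 comparison inside another trial's plan, and it is explained in SAP Section 4 and labelled in the outputs. What is missing is a cross-reference to the ALT-FLZ-401 objective. Adding it would be harmless, but it would move no estimate, interval, test or labelled conclusion.

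This rests on two assumptions: that results keep the strain name attached, as the planned titles do, and that the HAI results from this SAP are read as an H1 comparison, not as a statement about the whole quadrivalent vaccine. Nothing in the SAP says otherwise.
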